allow for exploratory analyses beyond the planned tests of implicit memory and executive function to assess for correlation between baseline cognitive function and ability to implement the behavioral therapy intervention. For instance, if the implementation of the behavioral intervention correlates with tasks of motor procedural learning, we might not expect it to correlate with tasks of declarative memory, thus providing further evidence that the task is one of implicit memory. Further, several of the tests have been linked with specific neuroanatomical regions of the brain and could provide preliminary data to support future studies involving functional imaging. The neuropsychological assessment will be repeated at visit 7 (12 weeks) in order to determine any change from baseline.

While solifenacin is a bladder-selective anticholinergic drug with less risk of negative cognitive impact than other anticholinergic bladder relaxants, the 12-week re-assessment of cognitive function in this study is important to understand the potential drug impact on cognition in the PD population. Persons with PD are at increased risk of developing cognitive impairment and are more susceptible to anticholinergic side effects of these medications (such as delirium, constipation, and dry mouth^{29,46-48}). Each testing session will last approximately 75 minutes, with breaks included to reduce fatigue. The measures are described below:

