1. The **SRTT** is a task of motor procedural learning in which participants are asked to press one of four keys on a response box which correspond to a lighted stimulus⁴⁹. Unknown to the participant, the light stimuli occur in a sequence and thus reaction time improves as the participant performs multiple blocks of the sequenced-based task. This learning is demonstrated by an increase in reaction time when the stimuli are presented in a random order after repetitions of the sequenced-based task. The task is typically measured in millisecond response times. The SRTT can be administered in approximately 30 minutes and has been used in multiple studies of procedural learning among PD participants^{50,51}. A response box for the SRTT is available for purchase from Psychology Software Tools Inc. The software to collect, store, and analyze the SRTT reaction times is also available for purchase from this company. A standard operating system installed on a laptop computer is sufficient to allow for data collection and initial analysis of reaction time. Once reaction times for the sequenced and random blocks have been calculated, these data will be entered into the Redcap database.
2. The **CERAD Word List subtest**⁵² requires the subject to recall 10 words that are presented over three trials, followed by short-delay recall and recognition memory. Left entorhinal cortex volume is significantly correlated with immediate recall on this task⁵³.
3. The **Nonverbal/Spatial Selective Reminding Test**⁵⁴ taps spatial memory by requiring the subject to recall a dot pattern. Performance on this measure has been found to discriminate patients with right versus left temporal lobe epilepsy⁵⁵.
4. The **Wisconsin Card Sorting Test**⁵⁶ will be used to assess hypothesis generation and response shifting. Perseverative errors on this task are related to the volume of prefrontal cortex and frontal white matter hyperintensities in adults 50-81 years old^{57,58}. Perseverative errors will be residualized on the total number of errors to control for overall level of performance.
5. The **Subject Ordered Pointing Task** will assess working memory. Subject Ordered Pointing is sensitive to middorsolateral prefrontal cortex lesions in monkeys and humans, and activates dorsolateral prefrontal cortex on positron emission tomography in normal adults.

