Power Analysis: The power analysis is informed by the ICIQ-OAB symptom score reduction observed in the BETTUR PD and BETTUR2 studies of behavioral therapy for urinary symptoms in PD. Based upon the bladder diary-derived UI frequency data (consistent measure used in both behavioral and drug trials), the effect of behavioral therapy and drug therapy to reduce UI frequency is similar. The ICIQ-OAB symptom score range is 0-16, with higher scores indicating worse symptoms. A score \geq 7 would indicate clinically significant OAB symptoms (urgency, frequency, urgency UI, nocturia) occurring on average at least *sometimes*. In our previous studies, we have observed a 2-3 point reduction in the symptom score, which represents a 12%-19% reduction from baseline^{24,64}. The minimally clinically important difference for the ICIQ-OAB is defined as a statistically significant reduction in the symptom score that is accompanied by a reduction in bother and improvement in OAB-specific QOL. Because the observed reduction **\geq 2 points** represents a statistically and clinically meaningful difference, we propose a non-inferiority margin of 15%. Thus, we will randomize 90 participants in order to complete the interventions in 80 participants, which assumes 85% power and a non-inferiority margin on the OAB symptom score of 15% at 12-weeks post-randomization. **Table 6 indicates that the proposed sample size will permit an assessment of non-inferiority within a range of potential non-inferiority margins that correspond to outcome assessments in our pilot studies.**

Standard Deviation of 12 week ICIQ-OAB Symptom Score	Margin of Non-Inferiority Between Groups at 12 weeks (Assumes OAB Symptom Score at baseline of = 8.1)				
	10%	12.5%	15%	20%	
	1.0	23	16	11	7
2.0	89	59	40	24	
3.0	198	131	88	52	

Table 7: Summary Outcome Assessments

Outcome Assessment	Baseline Visit 1/Visit 2	2 weeks Visit 3	4 weeks Visit 4	6 weeks Visit 5	8 weeks Visit 6	12 weeks Visit 7
ICIQ-OAB	X			X		X
7-day Bladder Diary (drug)	X			X		X
7-day Bladder Diary (behavioral)	X	X		X		X
7-day PFME Record (behavioral)		X				
ICIQ-OAB QOL	X			X		X
Benefit & Satisfaction				X		X
Life Space Assessment	X			X		X
Self Efficacy for Chronic Disease Management	X					X
Patient Global Symptom Control Score				X		X
Adverse Event checklist	X	X	X	X	X	X
Adherence Questionnaire		X		X		X
Neuropsychological battery	X					X
MDS-UPDRS	X					X

Data Analysis:

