Primary Outcome for Aim 1: To evaluate the impact of treatment within group, we will first use a random effects mixed model with adjustment for baseline OAB symptom severity to compare mean ICIQ-OAB symptom scores across the three time points. In order to test for non-inferiority of behavioral therapy compared to drug therapy, we will assess the difference in the mean 12-week post-randomization ICIQ-OAB symptom score between groups using a two-sample t-test, assuming a non-inferiority margin of 15% and a standard deviation of 2.0 points. The significance level of the test will be set at an α of 0.025 for a one-sided test of significance.

Secondary Outcomes: The pre-treatment and post-treatment frequency of UI based on the bladder diary will be used to calculate a percentage change for each participant ($[\text{pre-treatment frequency} - \text{post-treatment frequency}] / [\text{pre-treatment frequency}] \times 100\%$). Based on pilot study results, non-normality of the diary data is anticipated and thus the Wilcoxon rank sum test will be used for bladder diary-reported outcomes (UI, urgency, nocturia). Questionnaire-based secondary outcomes (ICIQ-OAB bother score, ICIQ-QOL, benefit and satisfaction, self-efficacy, voided volume, and the Life Space Assessment) will be assessed between groups using a t-test. Twenty-four hour voided volume measures will permit an evaluation of nocturnal urine production as a confounding factor for response to treatment among persons with nocturia. Nocturnal urine production includes the sum of all voided volumes after going to bed with the intention of sleeping and the subsequent first voided volume the next morning. Additionally, an evaluation of change in mean voided volume provides an objective measure of functional bladder capacity.

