To explore other potential characteristics of successful behavioral therapy implementation, we will examine baseline characteristics that differ between those in the behavioral therapy group who demonstrate at least a 2-point improvement (reduction) in ICIQ-OAB symptom score versus those who report less improvement. Baseline characteristics will include gender, age, PD severity as measured by the MDS-UPDRS motor part 3 score (mild vs. moderate), depression as well as the pre-specified measures of cognitive function (SRTT and Wisconsin Card Sort Test). Baseline characteristics will be compared using chi-square or t-tests as appropriate.

We will examine the correlation between cognitive function tests of procedural learning and executive function with change in ICIQ-OAB score after behavioral therapy. Performance on the SRTT will be assessed as the mean change in time (milliseconds) between random and sequential tasks. Performance on the Wisconsin Card Sort Test will be assessed using the perseverative errors score. We will correlate these measures with the change in ICIQ-OAB score between baseline and 12-weeks post-randomization.

Baseline characteristics which are significantly associated with successful implementation of behavioral therapy will be included as part of a multivariable logistic regression model including SRTT performance, Wisconsin Card Sort Test perseverative errors score in order to determine if these cognitive domains are important in the central nervous system control of OAB symptoms in response to behavioral therapy.

Aim 2b: Compared to exercise therapy, does anticholinergic drug treatment for urinary symptoms worsen executive function and PD motor symptom severity?

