Regardless of whether behavioral therapy proves to be inferior or non-inferior to drug therapy, understanding the potential association of drug therapy with cognition or PD motor symptom severity are important factors for patients and providers to determine next steps for treatment⁶⁹.

Measures: Participants in both groups will complete a baseline and 12-week neuropsychological battery as previously described including the MoCA test, SRTT, CERAD Word List subtest, Nonverbal/Spatial Reminding Test, Wisconsin Card Sort Test, and the Subject Ordered Pointing task. We will use the Anticholinergic Risk Scale⁴⁷ to calculate an overall anticholinergic drug score for participants in both groups based on medications listed at the randomization visit as a potential effect modifier. The MDS-UPDRS will be repeated at the 12-week visit. Thus, the behavioral therapy group will serve as a control group to assess the potential impact of solifenacin drug therapy on domain-specific cognitive function and PD motor symptom severity.

Data Analysis: [The analysis for aim 2b will generate data informing how central cognitive control of sensory integration and motor function are involved in the response to drug therapy.] Baseline and 12-week post-randomization cognitive tests will be evaluated using paired t-tests to assess for change within the drug group and two-sample t-tests for differences across groups (the behavioral therapy group will serve as a control for this analysis). Because cognitive impairment in PD most often manifests as impaired executive function, we will focus on tests of this domain, such as the Wisconsin Card Sort Test or the Subject Ordered Pointing Task in our evaluation of impact on cognition. The clock-draw test, as a component of the MoCA, is another assessment of executive function that is often performed in clinical practice. If changes are noted on domain-specific assessments of the neuropsychological battery, we will also examine correlation with clock draw scores obtained through the MoCA test. The Anticholinergic Risk Scale will be assessed based upon medications at randomization. The Anticholinergic Risk Scale score will be included in a multivariable model including baseline characteristics associated with changes in cognitive function in bivariable analyses.

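### The card-sort score for the Aim 2b harm comparison is not defined, and the battery's residualizing rule, if applied to week-12 total errors, would hide most of a general executive decline on that test

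*Combined protocol and SAP*

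**What the plan says.** Under Enrollment and Neuropsychological Assessment, item 4 sets the scoring rule for the Wisconsin Card Sorting Test: "Perseverative errors will be residualized on the total number of errors to control for overall level of performance". It does not say which visit's total errors are used, how the slope is fitted, or which aim the score serves. The same section states: "The neuropsychological assessment will be repeated at visit 7 (12 weeks) in order to determine any change from baseline".

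Aim 2b asks: "Compared to exercise therapy, does anticholinergic drug treatment for urinary symptoms worsen executive function and PD motor symptom severity". Its Measures paragraph refers back to the battery description, lists the card-sort test by name, and has both arms take it at baseline and week 12. Its Data Analysis paragraph says "we will focus on tests of this domain, such as the Wisconsin Card Sort Test or the Subject Ordered Pointing Task". It plans paired t-tests within the drug arm and "two-sample t-tests for differences across groups". No card-sort score is named there.

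Aim 2a, Data Analysis, does name one: "Performance on the Wisconsin Card Sort Test will be assessed using the perseverative errors score". Residualizing is not mentioned.

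**The concern.** Total errors are the sum of perseverative and other errors, so the adjusting variable contains the outcome. At week 12 it is also measured after treatment. For a baseline predictor, as in Aim 2a, removing the overall error level is defensible because it isolates perseveration. For a harm question the same step can remove the harm. If the drug raises all kinds of error together, the rise in total errors accounts for the rise in perseverative errors, and the residual shows little.

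Aim 2b is where the trial looks for cognitive harm from solifenacin, and the plan says the answer matters to patients and providers choosing treatment. A null card-sort result could be read as evidence of no executive effect when the score was not able to show a general one. The documents also describe the card-sort measure in two ways, residualized in the battery description and apparently raw in Aim 2a, and leave Aim 2b to choose between them.

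**Working it through.** **Inputs from the documents.** About 40 per arm, from "we will randomize 90 participants in order to complete the interventions in 80 participants" (80/2 = 40). The between-arm test is a two-sample t-test. The plan gives no effect size, SD, alpha or power for Aim 2b, so there is no planned figure to reproduce. The stated one-sided 0.025 belongs to the Aim 1 primary test.

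**Assumptions, not in the documents.** Two-sided alpha 0.05; the size and pattern of the drug effect; the correlation *r* between perseverative errors *P* and total errors *T*; and, in the second check, the spread of other errors *N* and a test-retest correlation of 0.6.

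**1. Equal rise of 0.5 SD in *P* and *T*, week-12 scores.** In SD units the slope of *P* on *T* is *r*. The arm difference in the residual is 0.5 − 0.5*r*, and the residual SD is √(1 − *r*²). Hence d′ = 0.5(1 − *r*)/√(1 − *r*²).

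| Assumed *r* | d′ by formula | Simulated d′ | Simulated power |
|---|---|---|---|
| raw score | 0.50 | n/a | about 60% (calculated) |
| 0.7 | 0.15/0.714 = 0.21 | 0.20 | 13% |
| 0.8 | 0.10/0.600 = 0.17 | 0.16 | 9% |
| 0.9 | 0.05/0.436 = 0.11 | 0.11 | 7% |

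The simulation (4,000 runs, 40 per arm) fits one residual regression over both arms. The treatment shift then enters the slope, so the simulated values fall slightly below the formula.

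**2. Written through the components.** Let *T* = *P* + *N* and b = cov(*P*,*T*)/var(*T*). The share of the perseverative effect that is retained is 1 − b(1 + ΔN/ΔP). Take SD(*N*)/SD(*P*) from 0.5 to 1.5 and a *P*–*N* correlation from 0.3 to 0.9.

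- *Same shift in SD units for P and N:* retained share −0.11 to +0.13. When the SDs are equal, b = 0.5 and the share is 1 − 0.5 × 2 = 0. For a 0.6 SD rise, analysed as change with each visit residualized on its own totals, simulated power is 5% to 8%, against about 83% raw. This check is harsher than step 1 because equal shifts in *P* and *N* move *T* by more than the same number of its own SDs. With equal SDs and correlation 0.5, *T* rises 1.2/√3 = 0.69 SD.
- *Half as many extra other errors as perseverative errors, equal SDs:* share 1 − 0.5 × 1.5 = 0.25; power 28% to 44%.
- *Purely perseverative rise:* share 0.26 to 0.65, but the residual SD shrinks too. The standardized effect is 0.67 to 2.26 times the raw one. Simulated power (equal SDs, correlation 0.5 or 0.7) is 80% to 95%, against 82% to 84% raw.
- *Residualizing both visits on baseline totals:* about 98% to 99% of a general effect is kept; power is about 88% to 90%.

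**3. Paired test in the drug arm.** If residuals are refitted at each visit over both arms, they sum to zero at each visit. With equal arms the drug-arm mean is then minus the exercise-arm mean, and the drug-arm mean change is half the between-arm difference in change. It can differ from zero, but it measures change relative to the pooled sample. Equal worsening in both arms would appear as no change.

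**The case against.** The strongest reply is that the plan never says the residualized score is the Aim 2b outcome. Residualizing appears once, Aim 2b names no card-sort score, and the only analysis section that names one calls it the perseverative errors score. This stands as far as it goes. However, Aim 2b refers back to the battery description, and the residual is the only card-sort scoring rule in that description. An analyst following the text could reasonably apply it.

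Second, the visit of the total errors is unstated, and baseline totals would avoid the problem. That is correct. The stated purpose, controlling for overall level of performance, fits same-session errors more naturally, but the finding has to stay conditional on that reading.

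Third, a reader might infer that the whole Aim 2b harm test is disabled. The documents do not support that. The card-sort test is one example in an open list. The Subject Ordered Pointing Task, the MoCA and the rest of the battery carry no residualizing rule, so a general decline could still show there. The pointing task is not a direct replacement, since the battery description assigns it working memory and assigns card sorting hypothesis generation and response shifting.

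Fourth, a reader might infer that residualizing hides any drug effect, or that the paired test cannot detect anything. Neither follows. A selective rise in perseveration, which the residual is meant to isolate, largely survives in the between-arm test. The drug-arm mean of pooled residuals need not be zero. In one assumed selective case (0.5 SD rise, *P*–*N* correlation 0.5, retest 0.6) the paired test still had 34% power, against 93% for the raw score.

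Finally, Aim 2 is labelled mechanistic and has no stated power. Even the raw score has only about 60% power at 0.5 SD, so a null result would be weak evidence of safety in any case. That limits the consequence but is no reason to keep a score that may lose most of the signal.

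**Conclusion.** The point holds in conditional form. The card-sort outcome for Aim 2b is undefined, and the battery description and Aim 2a describe the score differently. If the week-12 score is residualized on week-12 totals, a general executive decline is largely removed from this test: d falls from 0.50 to about 0.1 to 0.2, and power from about 60% to about 7% to 13%. Those figures rest on an assumed 0.5 SD rise in both perseverative and total errors, assumed correlations of 0.7 to 0.9, 40 per arm and two-sided 0.05. The component version, with other assumptions, removes at least 87% of a general decline. The finding covers only the card-sort component and only general decline. It is worth correcting because the score serves the trial's cognitive-harm question and the correction needs no new data.

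**What to change.** In Aim 2b, Data Analysis, name unresidualized perseverative errors at baseline and week 12 as the card-sort outcome. Report total errors beside them, by arm and visit, and state that the comparison is not adjusted for week-12 total errors.

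Keep the residualized score as a supportive description of selective perseveration, or as the baseline predictor in Aim 2a. Wherever it is used, state which visit's totals enter and how the slope is fitted. Then align battery item 4, Aim 2a and Aim 2b so that each says which score it uses.

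The cost is wording only, since both scores come from the same test administration. The downside is that the raw score is less specific to perseveration; keeping the residual as supportive covers this.

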We propose a three-site, RCT conducted at the Atlanta (lead site), Birmingham and Richmond VA medical centers to establish non-inferiority of pelvic floor muscle exercise-based behavioral therapy compared to drug therapy for urinary symptoms in adults with PD. Groups will be stratified by OAB symptom severity, PD motor symptom severity, gender, and site. We will randomize 90 participants in order to complete the study in 80 participants, assuming 85% power and a non-inferiority margin for the OAB symptom score of 15% at 12-weeks. **The primary outcome measure will be urinary symptom severity as measured by the ICIQ-OAB symptom score^{32,33}** collected at 3 time points during the study: baseline, 6 weeks, and 12 weeks. PFME-based behavioral therapy will occur over 3 visits conducted during the first 6 weeks as was performed in the BETTER2 PD study. Participants in the drug therapy group will also have 3 visits during the first 6 weeks in order to individually titrate solifenacin drug therapy according to a validated symptom scale. Solifenacin has been selected because this bladder-selective anticholinergic drug (less risk of cognitive side effects) is the only drug with published evidence of potential efficacy in PD³⁴. At baseline, randomized participants will undergo a brief neuropsychological battery adapted from our current study to assess cognitive factors that may predict a preferred treatment strategy. At the 12-week assessment, the brief neuropsychological battery and MDS-UPDRS will be repeated in order to assess any change associated with treatment allocation. Follow-up visits will occur at weeks 4 and 8 to ascertain side effects and assess treatment adherence.

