- Any unstable health condition expected to result in hospitalization or death within in the next 3 months as determined by site principal investigator.
- Hypersensitivity to drug class
- Contraindication to the study drug (solifenacain) including: narrow angle glaucoma, history of gastric retention, history of acute urinary retention requiring catheterization
- Current use of a bladder relaxant – permitted to enroll after one-week washout
- Hematuria on microscopic examination in the absence of infection. A urologic consultation will be recommended and enrollment will depend on clearance by a urologist and agreement by the site PI that entry into the treatment protocol is not contraindicated
- If on diuretic, dose should be stable for at least 4 weeks
- If taking an alpha-blocker, dose should be stable for at least 4 weeks
- If taking dutasteride or finasteride, dose should be stable for at least 6 months
- Women who are pregnant, or breast-feeding, or planning to become pregnant. *Women of child-bearing age must agree to use of birth-control while enrolled

Figure 1: Schematic of the Study Design

*Visits 1,2, and 7 will require in-person procedures. All other visits may be conducted by phone/telehealth.

During the first visit, potential participants will receive an explanation of the study procedures and complete informed consent to participate. Baseline assessments will include the following:

Baseline assessments:

1. **Seven-day bladder diary** includes daily participant-reported voids and incontinent episodes, with ratings of associated urgency, and wake time and bedtime to assess daytime frequency and nocturia. A single 24-hour frequency-volume chart will be included in the 7-day diary at baseline, week 6, and week 12. Participants will measure their urine output with each void for a 24-hour period (first void after rising until the first morning void the following day) using a receptacle marked in 25 mL increments.

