Randomization: At the second visit, eligible participants will be randomized to one of two groups: treatment with PFME-based behavioral therapy or solifenacin drug therapy. Participants will be stratified by site, gender, UI severity (< or \geq a score of 9 on the ICIQ-OAB), and PD motor symptom severity (MDS-UPDRS < 33 on the part 3 motor score)⁵⁹. Participants will be randomized through computer-generated block randomization in groups of six. Based on preliminary data showing these cut points approximate the means among our randomized participants, we do not anticipate four stratification variables will present a challenge to recruitment. While participants will not be blinded to treatment group, the interventionist will be blinded to the participant's performance on the neuropsychological tests and SRTT performance.

Data Management: Participants' assessment data will be kept in a locked cabinet behind a locked door at each site of the Birmingham/Atlanta GRECC and the Richmond PADRECC. Bladder diaries will be scored by a research assistant who is blinded to the assigned treatment group. Data from the Birmingham and Richmond sites will be uploaded to a secure VA server in the form of PDF documents scanned on a VA device behind the VA firewall. Deidentified data will be entered and verified in Redcap by research staff at the Atlanta site, which will ensure accuracy of the data. A standard form will be used to record the date and reason for all

exclusions and dropouts, and these data will also be entered into the master database. Four times per year the PI will meet with the Atlanta-based data manager to review accrual, data entry, and eligibility criteria and examine the database for outliers or database entry errors at each site. The Redcap database will then be converted and data analyses will be completed in SAS 9.4 (SAS Institute, Cary, NC). Additional details regarding confidentiality of patient data are included in the Human Subjects plan.

Specific Aim #1: Using a RCT, determine non-inferiority of pelvic floor muscle exercise-based behavioral therapy versus drug therapy for urinary symptoms in PD.

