Human Subjects Involvement and Characteristics: Men and women with PD recruited from the Atlanta, Birmingham, Richmond, and Philadelphia VAMCs as well as in the surrounding community. We propose randomizing 90 participants to either exercise-based behavioral therapy or drug therapy with Solifenacain. In order to complete the study in 80 participants, we anticipated having to screen approximately 180 PD patients to identify those with clinically significant OAB symptoms, and enroll approximately 45 participants in each group. These estimates are based on our experiences in the BETTUR PD and BETTUR2 pilot studies. In the BETTUR PD study, 33 individuals were screened to enroll 20 participants. Of the 20 participants who were enrolled, 17 completed the study demonstrating a 15% drop out rate once enrolled. To date, in the BETTUR2 study, we have screened 107 individuals to randomize 51 participants and have had 6 participants drop out (11.7% rate).

During FY16, 541 unique Veterans with PD were served by the Atlanta VA and surrounding CBOCs. For the BETTUR PD pilot, 14 of the 32 screened subjects were recruited from the Atlanta VA after mailing letters to 360 Veterans identified with a diagnosis of PD in the Metro Atlanta area in FY08. Recruitment was extended to a university-based movement disorders clinic to achieve the intended sample size of 20 enrolled subjects. For the BETTUR2 study, of the 65 persons who have undergone screening procedures thus far, 25 were Veterans and 40 were recruited from university-based movement disorders clinics in Atlanta and Birmingham in order to maximize the team's ability to recruit the intended sample size. Thus, we propose to recruit both Veterans and non-Veterans for the proposed study from the outset. The university affiliates in Atlanta (Emory), Birmingham (University of Alabama at Birmingham), Richmond (Virginia Commonwealth University), Philadelphia (University of Pennsylvania) all have active movement disorders programs, which enhance the overall resources available to the study.

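### A single printed block size of six, in an open-label trial with no stated allocation concealment, makes an expected 9 to 15 of the 90 allocations deducible with certainty by anyone keeping a tally for each stratum

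*Combined protocol and SAP*

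**What the plan says.** The Randomization section gives one block size: "Participants will be randomized through computer-generated block randomization in groups of six". It names four stratifiers, beginning "Participants will be stratified by site, gender, UI severity", the fourth being the MDS-UPDRS part 3 score. It justifies the two severity cuts by saying that "these cut points approximate the means among our randomized participants".

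On blinding, the same section says "While participants will not be blinded to treatment group". The blinding that is described covers other things: the interventionist and principal investigator do not see the cognitive and reaction-time results, and the bladder-diary scorer does not see treatment group (Enrollment and Neuropsychological Assessment; Randomization; Data Management).

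The target is in Research Design and Methods: "We will randomize 90 participants in order to complete the study in 80 participants". Human Subjects adds the ratio: "enroll approximately 45 participants in each group".

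The number of sites is inconsistent. Research Design and Methods says "We propose a three-site, RCT conducted at the Atlanta (lead site), Birmingham and Richmond VA medical centers", while Human Subjects adds Philadelphia as a fourth.

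Eligibility is settled and randomization takes place at the same visit, visit 2. The documents do not say who holds the list, how an assignment is released, or whether eligibility is locked first.

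**The concern.** In a 3:3 block of six, once one arm has received its three assignments the rest of the block is fixed. Because treatment is open and site is a stratifier, each site can see every past assignment in its own strata, and the protocol supplies the block size. Generating the list by computer or holding it centrally does not prevent the deduction, which uses only past assignments and the printed size.

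Advance knowledge matters if it can affect who is entered, or when. Some entry conditions involve judgment or timing. After unexplained hematuria, for example, entry needs urologic clearance and "agreement by the site PI that entry into the treatment protocol is not contraindicated". There are also a washout, dose-stability periods and a site-investigator judgment on unstable health.

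The primary outcome is a self-completed questionnaire in an unblinded trial, so concealment before entry is one of the few protections available. The non-inferiority comparison is a two-sample t-test of 12-week means. Baseline adjustment is stated only for the separate within-group mixed model, so a prognostic imbalance from selective entry would pass into the comparison unadjusted. The margin is small: 15% of 8.1 = 1.2 points.

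**Working it through.** **Inputs.**
- From the documents: block size 6, read as 3:3 within each stratum; 90 randomized 1:1; 3 × 2 × 2 × 2 = 24 strata with three sites, or 4 × 2 × 2 × 2 = 32 with four.
- Assumed, because the documents do not give them: 50% to 95% men, equal sites, and 50/50 splits on both severity cuts (suggested by the remark that the cuts lie near the pilot means).

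**The plan's own figure.** The documents give no figure for predictable allocations. The 90 is consistent with 80 completers: 80 / (1 − 1/9) = 90, and the pilot's 11.7% dropout gives 80 / 0.883 = 90.6, rounded up to 91.

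**One block.** There are 20 equally likely 3:3 sequences. An allocation is certain when one arm is already used up.
- Positions 1 to 3: probability 0.
- Position 4: first three alike, 2/20 = 0.1.
- Position 5: three of one arm among the first four, 2 × 4/20 = 0.4.
- Position 6: 1.
- Total per complete block: 0.1 + 0.4 + 1 = 1.5.

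**Whole trial.** For a stratum of n people, c(n) = 1.5 × (number of complete blocks) + the position probabilities reached in the unfinished block. The expected total is the sum over strata of E[c(n)], with n ~ Binomial(90, p) and p the stratum's share. A single unstratified list would give 15 × 1.5 = 22.5, and stratifying by site alone about 21. With 24 strata the mean stratum holds 90/24 = 3.75 people, so many blocks never fill and the total is lower.

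| Men | Certain, 24 strata | Certain, 32 strata |
|---|---|---|
| 50% | 8.5 | 5.0 |
| 80% | 11.9 | 9.0 |
| 95% | 15.2 | 12.7 |

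With three sites, weighting them 541:399:112 (the Veteran counts under Participants) and moving the severity splits to as much as 70/30 keeps the range at 8.5 to 15.5. Single trials vary around these means: the 95% range is about 4 to 14 with equal strata.

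**Mixed blocks.** I simulated 24 strata and 600 trials per setting. The observer knows all past allocations in the stratum and the set of possible sizes. Entries are fixed six versus mixed 4/6/8.

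| Men | Certain | ≥80% predictable | ≥75% predictable | Best-guess accuracy | Mean absolute arm imbalance |
|---|---|---|---|---|---|
| 50% | 8.5 vs 0.5 | 9 vs 5 | 16 vs 24 | 61% vs 61% | 4.6 vs 4.4 |
| 80% | 11.9 vs 1.0 | 12 vs 8 | 18 vs 26 | 63% vs 63% | 4.2 vs 3.8 |
| 95% | 15.2 vs 1.6 | 15 vs 11 | 21 vs 30 | 64% vs 64% | 3.4 vs 3.5 |

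Repeated simulations agree to within about one allocation and about half a person of imbalance.

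**The case against.** The strongest objection is that the benefit depends on counting only certainty. Staff can also act on a strong guess. Mixing the sizes leaves best-guess accuracy unchanged and increases the number of allocations predictable at 75% or more. This stands. If selection followed the number of correct guesses, changing block sizes alone would gain nothing.

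Four further limits also stand:
- The count is what a diligent tally of eight strata per site could reveal. A reader might infer that staff do know these allocations; the documents do not show that.
- The opportunity is narrow. The stratum needs the ICIQ-OAB form, collected at visit 2, and the motor score, which Baseline assessments places at the second visit and the Visit Schedule at visit 1. Most entry criteria are objective cut-offs. The quoted site-investigator agreement applies only to hematuria and also needs a urologist's clearance.
- Stratification limits what selection could achieve. Entry requires a score of at least 7 and the cut is at 9, so the lower stratum holds only scores of 7 and 8. Motor severity is stratified too.
- Dates and reasons for exclusions are recorded, and eligibility is reviewed four times a year, so selective exclusion would leave a trace. That helps detection but does not conceal the next assignment.

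The objection does not remove the basic gap: one size is printed, treatment is open, and no concealment step is described. A known next assignment is also a firmer basis for deferring someone than a guess that is right about six times in ten.

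**Conclusion.** The point holds as a low-cost improvement. With three sites, an expected 9 to 15 of 90 allocations (about 9% to 17%) could be deduced with certainty before the visit 2 eligibility decision; with four sites, about 5 to 13. Both ranges are upper bounds on usable knowledge. They rest on 3:3 blocks within every stratum, a complete tally, 50% to 95% men and even severity splits. The documents should settle whether there are three or four sites.

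Two stronger readings are not supported. One is that the primary comparison is biased: the calculation counts deducible allocations and estimates no effect on the ICIQ-OAB difference, and nothing in the documents shows selective entry. The other is that mixed blocks make allocation unpredictable: they nearly remove certainty, to about 0.5 to 2 allocations, but do not reduce guessing.

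**What to change.** For participants not yet randomized:
1. Generate the list with randomly mixed block sizes, for example 4, 6 and 8.
2. Keep the sizes out of the site-facing protocol and hold them in a restricted randomization document.
3. State who holds the list, and release each assignment only after eligibility has been entered and locked.

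Steps 2 and 3 are essential, given what mixing alone leaves open. Withholding the sizes denies staff the exact probabilities. The lock fixes the eligibility decision before the assignment is seen. Neither stops someone from guessing the arm that is behind in a stratum. If such a release procedure already operates, one sentence should say so.

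The cost is a new list and a short amendment. Arm balance hardly changes if mixed blocks run from the start. A change made mid-trial leaves some current blocks incomplete, in up to 24 strata (32 with four sites), and the imbalance figures above do not cover that. If randomization is already complete, report the scheme and compare baseline characteristics between determined and undetermined allocations.
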